8.1.2.2 CLINICAL VARIABLES AND BIOLOGICAL MARKERS

When available FeNO, peripheral eosinophils (the three highest values in the past 12 month) collected via CBC with Differential, total IgE, presence or absence of positive specific IgE results will also be recorded. Prior lung function measurements and spirometry data (all available within 12 months prior to initiation of biologic therapy) will be abstracted via the MiAsthma Registry when available. No study specific testing will take place (with the exception of home spirometry).

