5. To evaluate the asthma control and health care utilization of subjects as measured by the number of exacerbations (acute worsening of asthma requiring at least 3 days of corticosteroids or a doubling dose of maintenance steroids), Emergency and hospitalization encounters, and patient-reported perceptions of asthma control.
6. To employ machine learning techniques to a robust well characterized cohort with clinical, biological, and digital markers to develop a predictive algorithm aimed at identifying responders to biologics. In addition, we would aim to develop an algorithm that can detect early changes in measured parameters that can predict long-term improvements in asthma control and exacerbations when biologics are initiated. The latter objective will be achieved by focusing on the subgroup of patients initiating biologics for the first time or switching between biologics due to perceived inadequate response.

Endpoints:

Primary Endpoint:

Mean and median number of (daily) doses of ProAir® Digihaler™ and AirDuo® Digihaler™ utilized at baseline, temporal patterns in rescue and controller medication utilization, and within-patient parameter mean, median, and variance per-inhalation to establish baselines.

Secondary Endpoints:

1. Proportion of patients with different rates of adherence.
2. Proportion of Patients achieving non-response, partial-responses, and complete response to biologics.
3. Change in Main Peak Inspiratory volume from baseline up to one year.
4. Change in Mean Inspiratory Time from baseline up to one year.
5. Change in mean peak inspiratory flow (PIF) from baseline up to one year.
6. Change in mean forced expiratory volume in one second (FEV1) from baseline up to one year.

Exploratory Endpoints

7. Number of exacerbations from baseline up to one year.
8. Number of hospitalizations.

9. Number of emergency room visits.
10. Mean Asthma Control Test (ACT) scores.
11. Algorithm that produces a daily asthma exacerbation probability given a set of baseline and current inhalation parameters. A confusion matrix summarizing the algorithm's performance on training dataset and from which performance statistics (accuracy, sensitivity, specificity, etc.) can be computed.

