of oral corticosteroids (OCS). This exposure to OCS increases the odds of developing co-morbid diseases such as diabetes, hypertension, cardiac disease and cataracts¹. Severe asthma is associated with an increased risk of acute events/exacerbations that result in accelerated lung function decline² and increased morbidity and mortality. Exacerbations are difficult to characterize and what is currently known about the changes in lung function prior to, during, and after exacerbations is predominantly focused on expiratory flow and highly reliant on patient diaries and peak flow meters. The variability in inspiratory flow parameters during acute events is not well characterized and may significantly impact inhaled drug delivery. The Digihaler™ data could enable the development of next-generation asthma action plans and novel real-time asthma control monitoring. Furthermore, this technology will allow the development of novel methods to monitor asthma and enable earlier detection of acute asthma exacerbations. The early detection of asthma attacks would enable clinicians and empower patients to intervene and perhaps change the trajectory of illness.

The rapid development of new biologics approved for the management of severe asthma with type II inflammation has led to a revolution in asthma care³⁻⁵. The term "type II inflammation" refers to an increase in the levels of type II cytokines including interleukin IL-4, IL-5 and IL-13, which results in downstream production of IgE and eosinophils. Sixty percent of severe asthma patients have evidence of type II inflammation^{6,7}. Surrogate biomarkers including peripheral eosinophils, fraction of exhaled nitric oxide (FeNO) and total IgE levels are used to phenotype patients with severe asthma and to guide biologic drug selection⁸. Eosinophils have been shown to predict response to IL5 and IL4 targeted therapies and FeNO is a predictor of response to anti-IL4 therapy^{9,10}.

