5 STUDY POPULATION

5.1 INCLUSION CRITERIA

1. A history of severe persistent asthma as defined by ERS/ATS criteria which includes the presence of poor asthma control on high dose ICS/LABA OR the need for high dose ICS/LABA to maintain asthma control OR oral steroids for maintenance therapy for more than 50% of the prior year.
2. Age >18 years of age or older.
3. Presence of current biologic use or planned initiation of biologics following study enrollment.
4. Patients will be categorized on the basis of asthma control (ACT < 19 will be considered poor asthma control). We will cap the patients with good asthma control at 30% and will no longer enroll those patients once the strata have been fully enrolled.
5. Willingness to switch maintenance inhalers to AirDuo® Digihaler™ and/or to use ProAir® Digihaler™ for rescue therapy. Use of nebulized albuterol will be discouraged but not prohibited. We will require patients to document nebulizer use. Patients that discontinue Pro-Air will be asked to document use of their rescue inhalers in their diaries.
6. Can read and communicate in English and is familiar with and is willing to use his/her own smart device and download and use the study application. If their smart device is not compatible with the study software; willingness to use an alternative device that will be provided by the study team.
7. Ability to provide informed consent.
8. The patient must be willing and able to comply with study requirements and restrictions and to remain at the investigational center for the required duration during the study period, and willing to return to the investigational center for the follow-up procedures and assessments as specified in this protocol.

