5.5 STRATEGIES FOR RECRUITMENT AND RETENTION

Patients will be recruited from the Severe Asthma Clinics at the University of Michigan. The program currently has 300 patients receiving biologics for asthma. We will also recruit patients from other clinics that are receiving biologics as long as the providers are willing to obtain and document detailed information on biologic response to therapy.

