9 STATISTICAL CONSIDERATIONS

9.1 STATISTICAL HYPOTHESES

- Primary Efficacy Endpoint(s): Establish group-level daily/weekly baseline normative values for: (1) mean and median number of doses of ProAir® Digihaler™ and AirDuo® Digihaler™, and per-inhalation baseline normative values for (2) peak inspiratory flow (PIF), (3) inspiratory time and (4) volume. We will test the hypothesis that patient-specific baseline usage values are significantly different from usage values collected during or leading up to exacerbation events.
- Secondary Efficacy Endpoint(s): 1. Test the hypothesis that imminent exacerbation events can be predicted using Digihaler™ inhalation parameter measurements. 2. Test the hypothesis that PIF is linearly (or non-linearly) related to FVC and FEV1. Test the hypothesis that there exists a threshold for change in PIF that is associated with a clinically meaningful change (>10%) in lung function. 3. Test the hypothesis that patients with low, moderate, and high adherence to maintenance inhalers have significantly different asthma outcomes. 4. Test the hypothesis that non-responders, partial, and complete responders have significantly different Digihaler™ inhalation parameters. 5. Test the hypothesis that future response to biologics can be predicted using clinical, biological, and digital (inhalation) markers.

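### Eosinophils, FeNO and IgE are not tied to biologic start as spirometry is, so in patients already on a biologic these predictors may be partly or wholly on-treatment values

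*Combined protocol and SAP*

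**What the plan says.** Section 8.1.2.2 lists the biological markers to be recorded when available. For eosinophils the rule is "peripheral eosinophils (the three highest values in the past 12 month) collected via CBC with Differential". No reference date is given: it could be enrolment, biologic start, a study visit or the data extraction. FeNO, total IgE and specific IgE results stand in the same sentence with no window. The next sentence abstracts earlier lung function and spirometry, "all available within 12 months prior to initiation of biologic therapy".

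Four other places bear on this:

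- **Who is enrolled.** Section 5.1 requires "Presence of current biologic use or planned initiation of biologics following study enrollment". Section 5.5 describes the pool: "The program currently has 300 patients receiving biologics for asthma".
- **Why the markers are collected.** Section 2.1 states that "Eosinophils have been shown to predict response to IL5 and IL4 targeted therapies and FeNO is a predictor of response to anti-IL4 therapy". It also says that the biologics target type 2 inflammation, which it describes as raising eosinophils and IgE downstream, and that the aim includes predicting response a priori.
- **How they are used.** Section 9.1 includes: "Test the hypothesis that future response to biologics can be predicted using clinical, biological, and digital (inhalation) markers". The Synopsis (exploratory endpoint 12) and the Section 3 table also name biomarkers as inputs to the responder model.
- **Any restriction.** Synopsis exploratory objective 6 says: "The latter objective will be achieved by focusing on the subgroup of patients initiating biologics for the first time or switching between biologics". This applies to the early-change algorithm only.

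**The concern.** A baseline predictor of treatment response should be measured before the treatment. The plan follows that principle for lung function but not for the biomarkers, although both are specified in the same paragraph and feed the same model.

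In a new starter, a low eosinophil count describes the disease before treatment. In a patient who has been on a biologic for some time, the same count may show what the drug has done. Pooling the two gives one variable two meanings. In current users it can also carry part of the outcome into the predictor, because the response being predicted has already begun. A model built this way could not be relied on for a patient who has not yet started, which is the use that Section 2.1 has in mind.

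A secondary point concerns the number of tests. Keeping only the three highest values makes any summary of them depend on how many blood counts a patient happened to have. Section 1.3 (footnote 3) says that these tests are captured only if done clinically, so test counts are likely to differ between patients.

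**Working it through.** No sample size or power figure in the plan depends on this definition, so there is no stated number to reproduce.

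**1. The windows side by side (8.1.2.2)**

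| Variable | Window | Tied to biologic start? |
|---|---|---|
| Spirometry | 12 months before initiation | Yes |
| Eosinophils | Past 12 months, reference date not named | No |
| FeNO, total IgE | None given | No |

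**2. On-treatment share of the eosinophil window.** Assume that the look-back ends at enrolment, and let t be months on the biologic at that date (not given in the documents). The share is min(t, 12)/12:

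- t = 0: 0/12 = 0%
- t = 3: 3/12 = 25%
- t = 6: 6/12 = 50%
- t = 9: 9/12 = 75%
- t = 12 or more: 12/12 = 100%

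The answer depends on the unnamed reference date. If it were the week-48 visit, at which Section 1.3 also captures blood counts, a patient who started the biologic at enrolment would have 48/52 = 92% of the window on treatment.

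**3. Which values end up among the three highest.** This is a simulation for illustration. The assumptions are five counts at random times in the window, independent log-normal values with log-SD 0.5, and a treated-to-untreated ratio between 0.1 and 1.0. None of these comes from the documents.

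| Months on drug | Mean on-treatment share of the three highest | All three on treatment (share of patients) |
|---|---|---|
| 3 | 4–25% | 0.1–2% |
| 6 | 24–50% | 3–13% |
| 9 | 59–75% | 24–42% |
| 12 or more | 100% | 100% |

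The lower end of each range is the case in which the drug lowers counts strongly, so that picking the highest favours pre-biologic values. That protection is gone at 12 months.

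**4. Dependence on the number of tests.** Assume that the three values are averaged, which the plan does not say. The figures are medians relative to a patient with three tests and the same true level, for log-SD 0.3 to 0.7.

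| Correlation between a patient's values | 6 tests | 10 tests |
|---|---|---|
| Independent | 1.21–1.50 | 1.35–1.89 |
| 0.5 to 0.8 | 1.09–1.35 | 1.15–1.60 |

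**5. Is it corrected elsewhere?** Section 9.4.3 item 5, on the responder model, sets no restriction to new starters. No section asks for a pre-biologic biomarker value or for a flag separating treated from untreated values.

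**The case against.** The best defence is that 8.1.2.2 says what is recorded, not what is modelled. Section 9.4.9 leaves feature creation open, and an analyst could sort the values later. That would work only if enough had been recorded. Three values chosen for their size may leave out the pre-biologic ones, and nothing requires values from before the past 12 months.

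Other points stand in part:

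- First-time initiators are largely unaffected if the reference date is enrolment, because the two windows then nearly coincide. This is true, and it is why mixing them with current users matters.
- The early-change algorithm is already limited to initiators and switchers. This is also true, but the limit does not reach the main responder model.
- The Synopsis and the Section 3 table treat the responder model as exploratory, although 9.1 lists its hypothesis among the secondary ones. Section 9.4.3 item 5 does not name biomarkers, so the evidence that they are inputs rests on 9.1, the Synopsis and Section 3.

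A reader might infer that the window ends at enrolment and that every current user's eosinophil value is therefore a treated one. The documents support neither. The reference date is not stated, and under an enrolment date the values are certain to be all on treatment only after 12 or more months on drug. A reader might also infer from the pool of 300 that most of the 100 patients will be current users. The pool does not fix the enrolled mix.

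**Conclusion.** The mismatch is real, and nothing else in the documents resolves it for the main responder model. In patients already on a biologic, eosinophil, FeNO and IgE values may be partly on treatment. The eosinophil values are wholly so if the biologic was started 12 or more months before the reference date. Such values are not comparable with those of new starters and are unsuitable as a priori predictors.

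The size for the whole cohort cannot be computed, because the share of current users, their time on drug and the effect of each biologic on the markers are not given. It would go too far to say that the association with response will be reversed or erased: the documents give nothing from which to calculate that. It would also go too far to call eosinophils the key predictor, since Section 2.1 names FeNO as well. The test-frequency effect is secondary and rests on assumed inputs. The primary endpoint (inhaler use and inhalation parameters) is not affected. This is an inexpensive change that should be made, and the validity of the primary analysis does not depend on it.

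**What to change.** In Section 8.1.2.2:

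- Give eosinophils, FeNO and total IgE the window already used for spirometry: the 12 months before initiation of the biologic whose response is being classified.
- Abstract all available values with their dates relative to biologic start, instead of only the three highest. The summary then need not depend on how often blood was drawn.
- For patients who switch, flag values taken on a previous biologic.

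In Section 9.4.3 item 5, name the biomarkers as inputs and state that only pre-initiation values enter the a priori responder model as baseline predictors. Keep post-initiation values separate, for follow-up description and for the early-change algorithm, whose purpose is to use changes after the start of treatment.

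The cost is a change of wording and a longer look-back in the medical record for current users. No new test is needed. The drawback is that some long-term users will have no pre-biologic value on record and will be missing for that predictor. The number cannot be foreseen from the documents, so the report should give it for each marker.

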8.1.2.3 ASTHMA EXACERBATIONS

During the study, an asthma exacerbation will be defined as a worsening of asthma symptoms (defined below) that leads to any of the following:

- Administration of a bolus/burst of systemic corticosteroids (one dose of IV or IM steroids or at least consecutive three days of oral corticosteroids).
- An emergency room or urgent care visit for asthma related symptoms that required oral/IV/IM corticosteroids.
- An inpatient hospitalization (defined as admission to an inpatient facility and/or evaluation and treatment in a healthcare facility for ≥ 24 hrs) due to asthma.

For the protocol, the start date of the exacerbation will be based on the day of ER, urgent care visits or hospitalization. For those that did not experience one of these events, the day of the first dose of OCS will be used as the initial day of the exacerbation. The last day of systemic corticosteroids will be used as an end date of the exacerbation. If less than 7 days has elapsed between the end of the first exacerbation and the beginning of new symptoms, then this will be considered a relapse of the initial episode rather than a new episode. Subjects that experience exacerbations post enrollment will be treated per standard of care by the patient's physician.

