9.4.3 ANALYSIS OF THE SECONDARY ENDPOINT(S)

1. To develop an algorithm that can identify probable imminent exacerbation events using Digihaler™ inhalation parameter measurements, we will compare the performance of several different machine learning regression models. Since we expect our training set to be relatively small with a low event rate, we plan to use the entire inhalation parameter dataset for model training but will employ repeated k-fold cross-validation to reduce variance (over-fitting) and include non-linear features to reduce bias (under-fitting). Examples of features that could be computed and included in this model include but are not limited to: difference between current value and patient-specific 7-day moving average, difference between current value and patient-specific 24-hour moving average, 7-day sample entropy, 24-hour sample entropy, difference in Min-Max over last 24 hours, etc.

A logistic regression model would treat the outcome (exacerbation) as a binary (Yes/No) event. The output of this model would be a daily probability between 0 and 1 that an exacerbation event will occur within a certain period of time. Different models will be fit for different periods of time (e.g., 24, 48, 72 hours) and the performance of each model assessed and compared to others. A recurrent event survival model would treat the exacerbations as discrete events in time. The output of this model would be the predicted time (e.g., in decimal days or hours) until the next event. Other models may include convolutional and/or recurrent neural networks (RNN) with LSTM or GRU architecture with varied numbers of hidden layers.

2. To determine whether and how PIF is associated with FEV1 and FVC, we assess the linearity and strength of the relationship using scatter plots, calculate the paired correlations (Pearson, Kendall, and Spearman), and compute univariate linear regression equations with PIF as the predictor and FEV1 or

FVC as the response. If non-linearity is found, we will determine the appropriate PIF transformation or polynomial term to use in the regression. Regression summary statistics (e.g., R-squared, Mean Absolute Error, Coefficients, and p-values) will be reported.

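### Section 8.1.2.3 dates an exacerbation by the encounter even when steroids began earlier, and sections 1.1 and 3 carry a different definition of the event

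*Combined protocol and SAP*

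**What the plan says.** **Start date (section 8.1.2.3).** The rule is that "the start date of the exacerbation will be based on the day of ER, urgent care visits or hospitalization". Only for patients without such an encounter does the alternative apply: "the day of the first dose of OCS will be used as the initial day of the exacerbation". New symptoms that begin less than 7 days after the end of an episode count as a relapse of it.

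**Event definition (section 8.1.2.3).** Worsening counts if it leads to any one of three things:
- a steroid burst, meaning "one dose of IV or IM steroids or at least consecutive three days of oral corticosteroids";
- an inpatient hospitalization due to asthma, with no steroid condition;
- "An emergency room or urgent care visit for asthma related symptoms that required oral/IV/IM corticosteroids", with no minimum duration.

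**Event definition (sections 1.1 and 3).** A parenthetical inside an exploratory objective reads: "acute worsening of asthma requiring at least 3 days of corticosteroids or a doubling dose of maintenance steroids". Neither text refers to the other or says which governs.

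**Use of the label.** Section 9.1 lists as a secondary hypothesis: "Test the hypothesis that imminent exacerbation events can be predicted using" Digihaler measurements. Section 9.4.3 describes a model whose output is a "daily probability between 0 and 1 that an exacerbation event will occur within a certain period of time", and adds: "Different models will be fit for different periods of time (e.g., 24, 48, 72 hours". Prediction is also a secondary objective in section 1.1, although section 3 places it among the exploratory objectives.

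**The concern.** The prediction model is meant to warn of an attack before it is established, so the start date decides which days are labelled as before the event. Under section 8.1.2.3, two patients who start oral steroids at home on the same day get different onset dates if one of them is later seen in the emergency room. For that patient, some days labelled as pre-event lie on or after the day treatment began. A model can then be credited partly for recognising an attack that is already being treated.

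The second issue is counting. With two definitions and no ranking, the same records can give different numbers of exacerbations.

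**Working it through.** The plan attaches no figure to this point, so there is none to reproduce. The check has two parts.

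**1. Dating**

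Inputs: horizons of 24, 48 and 72 hours, taken as h = 1, 2, 3 days (section 9.4.3); one prediction per day (section 9.4.3); event date S at the encounter (section 8.1.2.3). The lag L, in days from first steroid dose to encounter, is an assumption because the documents give no values.

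The positive prediction days run from S-h to S-1, and the first dose falls on S-L. The share of positive days on or after the start of treatment lies between two bounds:
- lower bound, counting only days after the first-dose day: min(L-1, h)/h;
- upper bound, also counting the first-dose day: min(L, h)/h.

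| L (assumed) | 24 h | 48 h | 72 h |
|---|---|---|---|
| 1 | 0-100% | 0-50% | 0-33% |
| 2 | 100% | 50-100% | 33-67% |
| 3 | 100% | 100% | 67-100% |
| 4 or more | 100% | 100% | 100% |

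For example, L = 2 and h = 3 give min(1,3)/3 = 33% and min(2,3)/3 = 67%. The table describes one encounter-dated event, not a share of the study's events.

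The relapse rule limits the scope. If a home course qualified as a burst by itself and ended less than 7 days before the new symptoms, the episode can be read as keeping its first-dose date. The late date is clearest when the course was still running at the encounter or was too short to qualify alone.

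**2. Definition**

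| Episode | Section 8.1.2.3 | Sections 1.1 and 3 |
|---|---|---|
| Oral burst of 5 days | counts | counts |
| Single IM or IV dose, no encounter | counts | does not count |
| ER visit with 1 day of steroid | counts | does not count |
| Asthma hospitalization, under 3 steroid days | counts | does not count |
| Maintenance dose doubled for 1-2 days | does not count | counts |

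A doubling that lasts three or more consecutive days can be read as a burst under 8.1.2.3, so it is not a clear conflict. Patients on maintenance oral steroids are eligible (section 5.1), so doublings can arise.

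**3. Reach into the response factor**

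Take one 3-day oral burst and one separate single IM dose: 2 events under 8.1.2.3 and 1 under sections 1.1 and 3. With an assumed earlier count P, the reduction is (P-2)/P or (P-1)/P.

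| P (assumed) | 2 events | 1 event | 50% threshold |
|---|---|---|---|
| 1 | -100% | 0% | not met by either |
| 2 | 0% | 50% | differs |
| 3 | 33% | 67% | differs |
| 4 | 50% | 75% | met by both |
| 5 | 60% | 80% | met by both |

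The answers differ only at P = 2 and P = 3, and only under three conditions: the parenthetical is applied to the response factor, the two events are separate under the 7-day rule, and P does not itself change with the definition.

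**The case against.** The encounter date is a prespecified study convention, it can be verified in the medical record, and predicting an encounter is a legitimate target. Section 8.1.2.3 is a dedicated section with operative wording, while the other text is a parenthetical to an exploratory objective. The percentages above follow from an assumed lag and contain no trial data. Home steroid start dates may rest on patient report at roughly monthly contacts.

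Much of this stands. Section 8.1.2.3 is evidently the operative definition, so the mismatch bears mainly on the exploratory count. The reliability of home dates is a real but small cost, because the plan already relies on first-dose dates for every episode without an encounter. The objection does not remove the inconsistency: the plan uses two kinds of onset, and a later encounter decides which one applies.

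A reader might infer three stronger things that the documents do not support:
- *That model performance will be inflated.* Nothing in the documents shows how inhalation signals behave once steroids start, so performance could move either way.
- *That the baseline values are contaminated.* If the 14-day exclusion in section 9.4.2 is anchored on the start date, 14 - L days before the first dose are still excluded: 11 at L = 3. The usage comparison in section 9.1 pools data from during and before events, so a shift of a few days has little effect there.
- *That the responder classification is undetermined.* This needs all three conditions listed in the working.

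**Conclusion.** The concern holds in two limited parts.

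First, the start-date rule mixes two stages of an attack. For episodes treated with steroids before an encounter, it can place days on or after the start of treatment among the pre-event days of the prediction models. For a single affected event the share ranges from 0-33% (L = 1, 72 h) to 100%. This assumes calendar-day predictions and the stated lags. The study-level effect cannot be computed, and neither its size nor its direction is claimed.

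Second, the parenthetical in sections 1.1 and 3 does not match section 8.1.2.3. Doublings shorter than 3 days count only under the former. Single IV or IM doses, and encounters with fewer than 3 steroid days, count only under the latter. The main consequence is for the exploratory exacerbation count.

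Both parts should be corrected. Neither undermines the descriptive primary aim.

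**What to change.** For event derivation only, with no change to any treatment rule:

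1. Reconcile sections 1.1, 3 and 8.1.2.3 to one event definition. Apply it to the on-study count and, where records allow, to the earlier count.
2. Set the event start as the earliest of the first systemic steroid dose for that episode (oral, IV or IM; for maintenance oral steroid users, the first dose above maintenance), the ER or urgent-care visit, or the admission. Link a steroid course to an encounter by the 7-day relapse rule already in section 8.1.2.3. This also gives a start date to an IV- or IM-only episode without an encounter, which the present rule leaves undated.
3. Repeat the prediction models with the encounter date as a sensitivity analysis.

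The cost is wording in sections 1.1, 3 and 8.1.2.3, a sentence in 9.4.3, and one extra set of model fits. Section 6.5.1 already has dose, start and end dates recorded for concomitant medication, so no new data are needed. The downsides are that home start dates may be less certain than encounter dates and that model performance may change in either direction. Settle this before the initial analysis, which section 9.4.6 places at the point when half of the patients have completed six months, so that the label is not chosen after results are seen.
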